### 5.3.10.5 Total Days of CVC Use

Total days of CVC use is collected as the Number of Dialysis Sessions Using CVC Post Index Procedure on the CVC Usage page. When a participant has a chain of CVC placements where the Date of Placement of an exchanged CVC is within one day of the Date of Removal of the previous CVC, it is considered one CVC placement, and the corresponding total days of CVC use will be accumulated for that participant. This endpoint will be assessed on the AT population.

#### 5.3.11 DUS Juxta/Peri-Anastomotic Area and Perforator Vein Patency

Data will be gathered using DUS examinations to evaluate the presence and characteristics of thrombosis and stenosis within the juxta-anastomotic area (defined as the arterial area extending 5cm before and the venous area extending 5cm after the anastomosis) and peri-anastomotic area (defined as the venous area extending from the

juxta-anastomosis area to the start of the perforating vein) as well as within the perforator vein for all AT population participants through 6 weeks.

Juxta/Peri-Anastomotic Area and Perforator Vein Patency will be collected on the Core Lab Analysis - Duplex Ultrasound: EndoAVF Arm page. Patent is defined as there is no evidence of occlusion or stenosis ≥ 50% as noted by DUS imaging. If the result from the Core Lab Analysis - Duplex Ultrasound: EndoAVF Arm page is not available, use the corresponding information from the Duplex Ultrasound: EndoAVF Arm for this analysis. The Juxta/Peri-Anastomotic Area and Perforator Vein Patency data will be summarized by descriptive statistics for the AT population.

#### **5.3.12** Wrist Arterial Procedure Access Considerations

A separate SAP will address these considerations.

#### 5.3.13 Participant Satisfaction and Quality of Life (QoL)

The Short Form-Vascular Access Questionnaire (SF-VAQ) and the European Quality of Life-5 Dimensions (EQ-5D) will be used to gather data on the participants QoL at the Screening/Baseline, 6-weeks, 6-, 12-, and 24-months follow-up visits.

The SF-VAQ has four domains: overall satisfaction (one item), physical symptoms (four items), social functioning (four items), and complications (four items). The score with the 7-point scale will be used for each item: 1= Strongly Disagree, 2= Somewhat Disagree, 3=Disagree a Little, 4= No opinion, 5= Agree a Little, 6= Somewhat Agree, and 7 = Strongly Agree. The score will be summarized with descriptive statistics for each item and each domain at the Screening/Baseline, 6-week, 6-, 12-, and 24-month follow-up visits for the AT population. Change in score from the baseline value will also be summarized for each follow-up visit.

The EQ-5D-5L measures five dimensions of health: Mobility, Self-Care, Usual Activities, Pain/Discomfort, and Anxiety/Depression. Data and change from baseline value will be summarized at each visit for each of the five health domains and Subject's Own Health State for the AT population.

## 5.3.14 HD AV Access Continuity

HD AV access continuity is defined as the ability for a participant to receive an alternate HD AV access in the same arm as the index AVF. This endpoint applies to AT population participants for whom their index AVF is abandoned. The alternate type(s) of HD AV access(es) placed in these participants will be collected.

The participants for whom their index AVF is abandoned or in whom they have access discontinuation will be identified if:

On the EndoAVF Abandonment eCRF page, Reason for Abandonment is not NULL.

Ana

On the Post-Procedure Intervention eCRF page, the question of "Was a New Vascular Access Created" is checked as Yes.

The counts and percentages of the alternate type(s) of HD AV access(es) will be summarized.

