Data will be gathered using DUS examinations to evaluate the presence and characteristics of thrombosis and stenosis within the juxta-anastomotic area (defined as the arterial area extending 5cm before and the venous area extending 5cm after the anastomosis) and peri-anastomotic area (defined as the venous area extending from the juxta-anastomosis area to the start of the perforating vein) as well as within the perforator vein for all participants through 6 weeks.

• Wrist Arterial Procedure Access Considerations

Data will be gathered using DUS examinations to evaluate the presence and characteristics of thrombosis and stenosis in arteries at the wrist used for procedure access during the index procedure. Images from these DUS examinations will be submitted to the Core Lab for review and assessment. Additionally, data will be captured for these participants on procedure-related AEs that are attributable to arterial access at the wrist as adjudicated by the CEC.

• Participant Satisfaction and Quality of Life (QOL):

The Short Form-Vascular Access Questionnaire (SF-VAQ) and the European Quality of Life-5 Dimensions (EQ-5D) will be used to gather data on the participants QOL at the time points specified in Section 1.3 and Section 6.

• HD AV Access Continuity

HD AV access continuity is defined as the ability for a participant to receive an alternate HD AV access in the same arm as the index AVF. This endpoint applies to participants for whom their index AVF is abandoned. The alternate type(s) of HD AV access(es) placed in these participants will be collected.

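### SAP 5.3.14 selects the wrong participants for HD AV access continuity and uses no arm variable, so its table will not show same-arm continuity among those who abandoned the index AVF

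*SAP*

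**What the plan says.** Protocol 4.3 describes the endpoint as "the ability for a participant to receive an alternate HD AV access in the same arm as the index AVF" and limits it: "This endpoint applies to participants for whom their index AVF is abandoned". It adds that the types of alternate access placed will be collected. The opening paragraph of SAP 5.3.14 agrees and names the analysis set: "This endpoint applies to AT population participants for whom their index AVF is abandoned".

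The SAP then gives an operational rule, which begins "The participants for whom their index AVF is abandoned or in whom they have access discontinuation will be identified if". Two eCRF conditions follow. The first is "On the EndoAVF Abandonment eCRF page, Reason for Abandonment is not NULL". The second is a Yes to the Post-Procedure Intervention question "Was a New Vascular Access Created". The word joining them is garbled in the text available and is read here as *And*. The planned output is counts and percentages of the alternate AV access types.

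**The concern.** The rule does not select the population that the same section has just defined, and it does not use the arm, which is what defines the endpoint. A reader of the report would see a table headed HD AV access continuity. It would leave out participants who abandoned the index AVF and got nothing in its place, include some whose AVF was not abandoned, and not separate same-arm from other-arm accesses. What is at stake is whether this table describes the stated endpoint. No hypothesis test is involved.

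**Working it through.** The plan states no rate, count or precision for this endpoint, so there is no figure to reproduce. The check sets the definition beside the rule and then uses assumed counts to show the effect.

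| Element | Definition (Protocol 4.3; SAP 5.3.14, opening paragraph) | Rule and output (SAP 5.3.14, remainder) |
|---|---|---|
| Population | Index AVF abandoned (SAP: within the AT population) | Abandoned or access discontinuation; any non-missing reason |
| New access | The thing to be observed | A condition of being selected |
| Kind of access | AV access | Any vascular access in the filter; AV access types in the output |
| Arm | Same arm as the index AVF | No variable named |

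**Population.** SAP 2.7 uses access discontinuation for a stop in use that fails the abandonment definition, and equates it with temporary interruption. Protocol 4.4 treats the two as mutually exclusive. The first condition lets discontinuations in, because it asks only that a reason be recorded. SAP 5.3.7 is stricter: it requires a date of abandonment, three salvage questions answered so as to rule out rescue of the access, and one of two named reasons.

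**Selection on the outcome.** With the conditions joined by *And*, a participant who abandons and receives no new access fails the second and is not identified. If *Or* were meant, the rule would admit participants with a new access and no abandonment record, which fits the definition no better.

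**Arm.** Neither the rule nor the output names a limb. The SAP does make a same-limb summary elsewhere (6.8), but for baseline AVG and AVF history.

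**Illustration (all counts assumed).** Let A be participants who abandoned, N those of A with a new access, and S those of N in the same arm. Let D be participants with discontinuation only whom the rule selects, and d those of D with a same-arm access.

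- Share matching the definition's population: S/A.
- Share in the rule's set, if the arm were added to it: (S + d)/(N + D), with d from 0 to D.

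| A | N | S | D | S/A | Rule's set, d = 0 | Rule's set, d = D |
|---|---|---|---|---|---|---|
| 30 | 24 | 18 | 4 | 60.0% | 18/28 = 64.3% | 22/28 = 78.6% |
| 30 | 18 | 12 | 4 | 40.0% | 12/22 = 54.5% | 16/22 = 72.7% |
| 30 | 12 | 6 | 4 | 20.0% | 6/16 = 37.5% | 10/16 = 62.5% |
| 30 | 18 | 12 | 0 | 40.0% | 12/18 = 66.7% | 12/18 = 66.7% |
| 30 | 18 | 12 | 10 | 40.0% | 12/28 = 42.9% | 22/28 = 78.6% |

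The fourth row isolates the loss of participants without a new access: S/N cannot be below S/A, because N cannot exceed A. Adding discontinuations can push either way. With N = 18, S = 12 and d = 0, the share falls to 12/(18 + 12) = 40.0% at D = 12 and below that for larger D. The overall direction of error is therefore not fixed. Adding an arm field alone would not repair the rule.

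**The case against.** The strongest reply is that the protocol never makes this endpoint a proportion. Other endpoints in Protocol 4.2 and 4.3 are worded as proportions; this one describes an ability and says that access types will be collected. The SAP's counts and percentages of types deliver that second part, and SAP 5.3.14 states no denominator. On this view the rule merely picks the cases to tabulate, and abandonments and interventions are summarised separately in the AT population (SAP 6.16 and 6.14). This stands in part: the type listing has descriptive value, and abandonment is not lost from the report altogether. But 5.3.14 does not link to those summaries, and its rule still contradicts its own opening paragraph on who belongs.

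Several stronger readings are tempting and are not supported:

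- That the SAP would report continuity in everyone selected. It plans a table of access types, not a continuity rate.
- That catheters would be reported as continuity. Protocol 2.1 counts a CVC as a vascular access, so one could pass the filter, but the output sentence is confined to AV access types.
- That the arm is not collected. Appendices 1 (shells) and 2 (derived data specification) are listed by title only; an arm variable or a different denominator there cannot be excluded.
- That arm preservation is a claimed benefit of the device. Protocol 9.2 does not list it.
- That the earlier 6-month cumulative patency of 77.3% (Protocol 2.1.2) gives the number of abandonments to expect. It is a Kaplan-Meier estimate at one time point, while follow-up here runs to 24 months with assumed attrition of 20%, 40% and 60% at 6, 12 and 24 months.

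A fair point also bears on the remedy. Some who abandon will die, receive a transplant, move to PD or leave the study, and may never have needed another access. Counting them silently as failures would mislead.

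**Conclusion.** The point holds as an internal contradiction and a wrong selection rule, not merely missing detail. Followed as written, SAP 5.3.14 tabulates re-accessed participants, mixes in temporary interruptions, and does not show same-arm continuity among those who abandoned the index AVF.

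The size in this trial cannot be stated, because the documents give no counts; the percentages above only show that the gap can be material. The conclusion rests on reading the garbled connector as *And* and on the SAP body alone. It does not require the protocol endpoint to be a formal proportion: the mismatch of population and arm exists either way.

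The consequence is small. The endpoint is exploratory, and Protocol 7.6 allows exploratory endpoints to go unreported. No primary or secondary conclusion is affected.

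**What to change.** Reword SAP 5.3.14 as follows.

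1. Population: AT participants meeting the permanent-abandonment criteria of SAP 5.3.7, with no requirement for a new access. The version in SAP 5.2.4 is less suitable because it also requires prior 2-needle use.
2. Main summary: number and percentage of these with a new AVF or AVG in the same arm as the index AVF, with a Clopper-Pearson interval. State that this measures receipt, as the observable form of ability.
3. Then list the types of alternate AV access placed.
4. Show separately those who abandoned and had no new access, including death, transplant, PD or study discontinuation after abandonment.
5. Show participants with temporary interruption only in a separate line, outside the percentage.

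The cost is SAP wording and a matching change to the table shells. Protocol 4.4 already keeps participants with an abandoned AVF in follow-up through 24 months with interventions collected, so no new visits are needed. The one practical item is the arm of the new access: confirm that the intervention eCRF captures it, or add the field and complete it for participants already re-accessed.

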## 6 Summary of General Investigation Data

## 6.1 Participant Disposition

The summary of the number of participants enrolled, intent to treated (ITT), as treated (AT), investigation device inserted but participant not treated, completed the investigation, and discontinued from the investigation by reason of discontinuation will be provided. Screen failures will be summarized for each inclusion/exclusion criteria that were not met.

#### 6.2 Deviations

The major or minor deviations will be classified as in Appendix 3. The number of participants with deviations and major deviations will be summarized with descriptive statistics by nature of the deviation by treatment. Deviations will be listed with date of occurrence and the nature of deviation. This summary will be reported based on the ITT population. A separate listing for eligibility violations/deviations (on the Eligibility Verification, the question of "Did Subject meet ALL Eligibility Criteria" is marked as No, and on the Screen/Baseline Subject Disposition eCRF page, Subject's Treatment Status is selected as "Study Device Inserted") will be generated.

## 6.3 Demographics and Baseline Variables

Demographics and baseline characteristics will be summarized with descriptive statistics using the AT population. Summary statistics for categorical variables will include frequency counts and percentages and for continuous variables will include mean, standard deviation, minimum, median, and maximum.

Demographics and baseline characteristics variables include:

- Age at Time of Informed Consent (year)
- Sex (Male, Female)
- Ethnicity (Hispanic/Latino, Not Hispanic or Latino)
- Race (American Indian or Alaskan Native, Asian (including subcategories), Black or African American, Native Hawaiian or Other Pacific Islander, White and Other)
- Height (cm)
- Weight (kg)
- Body Mass Index (BMI, kg/m^2)
- Radial Pulses
- Motor Deficit

## 6.4 Physical Exam

Physical exam will be collected at the Screening/Baseline, Discharge, 30 Day, 6 Week, 6 Month, and 12 Month visits. Physical exam data will be summarized for each visit for the AT population.

## 6.5 Vital Signs

Vital signs will be collected at the Screening/Baseline, Discharge, 30 Day, 6 Week, 6 Month, and 12 Month visits. Vital signs and the change from screening/baseline will be summarized for each visit for the AT population. Note:

The vital sign measurements on the non-target limb (recorded on the Procedure Overview eCRF page) will be used as the baseline value for the comparisons.

#### 6.6 Concurrent Illnesses and Medical Conditions

The participant's medical history (including Risk Factors, Kidney Disease, Cardiovascular Disease, Other Disease) will be summarized for the AT population.

## 6.7 Prior and Concurrent Medications

Not applicable.

## 6.8 AVG and AVF History

The AVG and AVF history data at screen/baseline will be summarized with descriptive statistics for the AT population. A separate summary will be provided for the AT population showing accesses in the same limb as the endoAVF.

## 6.9 Dialysis History/Onset

The Dialysis History/Onset data will be summarized with descriptive statistics for the AT population.

### 6.10 Device Failure, Malfunctions and Defects

Device deficiencies/malfunctions will be tabulated by the failure code. This summary will be reported based on the ITT population.

#### 6.11 Procedure Overview

The procedure overview data will be summarized with descriptive statistics for the AT population.

#### 6.12 Duplex Ultrasound

The duplex ultrasound data for both site-reported and core lab will be summarized with descriptive statistics for each visit for the AT population.

## 6.13 Hemodialysis/AV Access Circuit Assessment

The Hemodialysis/AV access circuit assessment data will be summarized with descriptive statistics for each follow-up visit for the AT population.

#### **6.14 Post Procedure Interventions**

The post procedure interventions data will be summarized with descriptive statistics for the AT population.

#### 6.15 Second Stage Procedures

The second stage procedures data will be summarized with descriptive statistics for the AT population.

#### 6.16 EndoAVF Abandonment

The EndoAVF abandonment data will be summarized with descriptive statistics for the AT population.

## 7 Safety Analysis

#### 7.1 Adverse Event

An AE is defined as any untoward medical occurrence, unintended disease or injury, or untoward clinical signs (including abnormal laboratory findings) in participants, users, or other persons, whether or not related to the WavelinQTM EndoAVF System and whether anticipated or unanticipated. This definition includes events related to the procedures involved. For users or other persons, this definition is restricted to events related to the use of the WavelinQTM EndoAVF System.

A separate CEC (Clinical Events Committee) will be formed to adjudicate AEs as defined in their respective charter. AEs will be adjudicated for seriousness and relatedness as reported by trial investigators. This does not apply to the user AEs.

An overall summary including the number and percentage of participants with at least one AE, total number of AEs, total number of SAEs, AEs by relationship to the Device/Index Procedure (Including Wrist Arterial Procedure Access, Embolization Device, and Closure Device)/AV Access Circuit, and AEs by severity of the event will be summarized for the ITT participants. In addition, the following summary tables will be provided:

- Number of AEs by System Organ Class (SOC) and Preferred Terms (PT)
- Number of SAEs by System Organ Class (SOC) and Preferred Terms (PT)
- Number of AEs by relationship to Study Device by System Organ Class (SOC) and Preferred Terms (PT)
- Number of AEs by relationship to Procedure by System Organ Class (SOC) and Preferred Terms (PT)
- Number of AEs by severity by System Organ Class (SOC) and Preferred Terms (PT)

A listing of all AEs, as well as of the SAEs and UADEs will be provided.

# 9 SAP Revision History

Version Number	Rationale for Change	Section or Page Affected	Description of Change
1.0	Original SAP		

# 10 Appendix

Appendix 1.1 Tables/Listing/Figures Shell for 6-Month Reporting

Appendix 1.2 Tables/Listing/Figures Shell for Final Reporting

Appendix 2 Derived Data Specification

Appendix 3 Deviations: Major/Minor Classification
